3.2 Rationale for Study Design

As described in [Section 1.1](#), BV is a major clinical concern, and new effective interventions not associated with antibiotic resistance and major drug interactions would be valuable additions to the current treatment arsenal. This study aims to investigate the clinical performance and safety of the Gedea Pessary containing GDL and NaG in treating BV.

Previous *in vitro* data show that GDL inhibits both bacterial and fungal biofilm formation (see [Section 1.2](#)). In addition, a device comparable to Gedea Pessary with regards to its pH-lowering and biofilm-inhibiting properties, have shown high BV cure rates.³⁸ Data also indicate that GDL is tolerable and does not pose any special risk to humans ([Section 1.3.1](#)).

Based on this, it may be argued that a trial involving patients is justified due to the widespread clinical problem of BV and the issues involving current therapies (see [Section 1.1](#)). Further, due to that the pessary has not been evaluated clinically prior to this study and the lack of proper comparators, a single-arm design has been chosen, allowing evaluation of clinical performance in a smaller number of patients. The risk of introducing assessor bias due to the open-label design have been minimized by the use of well-defined and documented scales, as well as objective laboratory assessments.

The dose of 300 mg GDL and 376.5 mg NaG administered 2 days apart on Day(s) 0, 2, 4, and 6^a was chosen based on pre-clinical data, specifically an *in vitro* dissolution test of the Gedea Pessary using a vaginal fluidic model (see IB). Measurements of pH in the *in vitro* dissolution test showed a pH-decrease duration of approximately 45 hours.

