- Refrain from using any intravaginal products (i.e., contraceptive creams, gels, foams, sponges, lubricants, or tampons, etc.) during the study period
- Refrain from sexual intercourse or use a condom until Day 7
- Signed informed consent and willing and able to comply with all study requirements

Exclusion Criteria:

- Patients with known or apparent signs of other infectious causes of BV (vulvovaginal candidiasis, *Trichomonas vaginalis*, *Neisseria gonorrhoeae*, *Chlamydia trachomatis*, *Herpes simplex*, or human papillomavirus) at screening
- Anticipated menstruation during the treatment period (Day 0 till Day 7)
- Patients who are pregnant or breastfeeding
- Patients who were treated for BV within the past 14 days
- Patients who are currently receiving antibiotic therapy unrelated to BV or have received antibiotic therapy within the past 14 days
- Patients who have used pH-modifying vaginal products within the last 14 days
- Patients who have received an investigational drug in a clinical investigation within 30 days prior to screening
- Known/previous allergy or hypersensitivity to any product constituent
- Any medical condition that in the Investigator's judgments would make the patient unsuitable for inclusion

Investigational Product, Dose, and Mode of Administration:

Gedea Pessary, containing 300 mg GDL and 367.5 mg NaG, administered vaginally.

Study Duration:

Up to 5 weeks for each patient, planned first patient in December 2018.

Criteria for Evaluation:

Primary endpoints:

- Clinical cure rate on Day 7.
 - Defined as absence of all of the following 3 Amsel criteria:
 1. Thin, white, yellow, homogenous discharge
 2. Clue cells on microscopy (more than 20% of epithelial cells)

3. Release of fishy odor “i.e. a positive whiff test” when alkali (10% potassium hydroxide [KOH] solution) is added

- Safety and tolerability, based on reported treatment-emergent AEs

Secondary endpoints:

All patients

- Proportion of patients being negative for each of the 3 Amsel criteria on Day 7 compared to Day 0
- Proportion of patients having a reduction in the sum of the 3 BV symptoms scores (fishy smell, burning, and irritation) on Day 4 and Day 7, compared to Day 0
- Change in the sum of the 3 BV symptoms scores (fishy smell, burning, and irritation) from Day 0 to Day 4 and Day 7
- Usability, measured by patient questionnaire

For patients not receiving prolonged treatment

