3.2.1 Risks and Benefits

The investigational device, Gedea Pessary has been evaluated in accordance with ISO 10993 (Biological Evaluation of Medical Devices). The evaluation included: cytotoxicity testing (Direct cell contact test, ISO 10993-5); *in vivo* irritation (Vaginal acute irritation; ISO 10993-10); and sensitization (local lymph node assay, ISO 10993-10). The *in vitro* cytotoxicity test, classified the test item as slight to moderate cytotoxic (scale 1–2 on a 3-grade scale); the *in vivo* irritation test as well as the *in vivo* sensitization test showed no signs of irritation, necrosis, or sensitization after treatment with Gedea Pessary.

The vaginal pessary may, in similarity with other vaginally administered products, cause temporary minor discomfort at insertion. The vaginal sampling procedures are similar to sampling procedures used in clinical practice and are unlikely to cause any major inconvenience to patients. In the Laccure pessary study,³⁸ there were no SAEs and vaginal itching was the most common AE.

There is a risk that patients will have no clinical benefit from the investigational device. This may cause patients to experience symptoms of BV including vaginal fishy smell, burning or irritation, pain during sexual intercourse, pain or discomfort when urinating, or abnormal vaginal discharge longer than necessary. However, an antibiotic will be offered on Day 14 if any symptoms should still be present, thus avoiding any risk associated with long-term untreated BV.

Subjects included in the study must refrain from using other intravaginal products to mitigate any risk of interactions with concomitant vaginally-administered products. The investigational

^a And on Day(s) 7, 9, 11, and 13 if receiving prolonged treatment

Protocol Version 2.1, 27 Jun 2019

LINK Medical Research | Protocol template

Version 2.0 | Effective date 17Apr2018

device acts locally on the vaginal mucosa and most likely will most likely not affect any concomitant systemic treatment.

Taken together, as the anticipated levels of discomfort are transient and mild, and that risks associated with long-term untreated BV are avoidable, the use of the investigational product appears to offer clinical benefits at a reasonable risk level.

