3.5.5 Day 7 (+2 Days); Follow-up Visit

Patients will visit the clinic on Day 7 to have gynecological examination performed where the Investigator or an authorized designee will assess the presence of BV according to 3 Amsel criteria. Vaginal samples will be collected by swab to be used for vaginal microbiome sequencing analysis and vaginal pH assessed for product *in vivo* duration.

If BV symptoms are still present according to Amsel's criteria, patients will have prolonged treatment and receive additional doses of investigational product to be administered at home on Day(s) 7, 9, 11, and 13.

In addition, patients will be asked questions from the patient questionnaire to assess: symptoms of BV (fishy smell, irritation, and burning); usability; concomitant medications; and AEs, if any.

Procedures performed:

- Gynecological examination by Investigator or an authorized designee assessing the presence of BV according to the following Amsel criteria:
 - Presence of thin, white, homogenous discharge
 - Presence of clue cells on microscopy (more than 20% of epithelial cells)
 - Release of fishy odor "i.e. a positive whiff test" when alkali (10% potassium hydroxide [KOH] solution) is added
- Symptoms of BV (fishy smell, irritation, and burning) evaluated by patients according to a scoring scale (0-3)
- Vaginal swab for sequencing
- Vaginal pH
- Recording of:
 - concomitant medications,

- adverse events, and
- usability
- Treatment dispensing and self-administration by patients if receiving prolonged treatment

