5 TREATMENTS

5.1 Investigational Product

The investigational product, Gedea Pessary (commercial name *pHyph*), is a GDL-and-NaG containing pessary to be administered vaginally with a CE-marked vaginal tablet applicator (Schägner GmbH, Steinmauern, Germany). The device is intended to treat vaginal bacterial and Candida infections, see [Figure 2](#) and [Figure 3](#) for product image and applicator label. Gedea Pessary is a Class IIa medical device according to MDD 93/42/EEC (the Swedish regulation SFS 1993:584 and LVFS 2003:11).

NOTE: The terms investigational product, Gedea Pessary, investigational device, pessary, and vaginal pessary are used interchangeably in the CIP.

Gedea Pessary is a white, convex, bullet-shaped tablet, approximately 2 cm in length, contract-manufactured by Galenica AB (Malmö, Sweden). The pessary is slow-release formulated, administering 300 mg GDL and 367.5 mg NaG over 45 hours. Each patient will administer a total of 4 pessaries in the study or 8 if receiving prolonged treatment. The investigational products will be packed in blister packs containing 4 pessaries labeled with *Gedea Pessary* and batch number. Blisters will be packed together with 4 vaginal tablet applicators in a cardboard-box labeled with *Gedea Pessary, for investigational use only*, production date, and expiry date ([Figure 4](#)).

It is the responsibility of the Investigator to ensure that the investigational products are stored in their original packaging in a secure location with access only by authorized personnel, separate from other medications. The investigational product shall be stored at room

temperature (15°C-25°C), protected from direct sunlight or freezing. The investigational products *must not* be used outside of the study. For further reference, refer to the IB.

Instructions for use will be distributed at the first visit, advising patients on how to use the product together with the applicator. Briefly, patients will be instructed to: wash their hands and vaginal area prior to use; place a tablet into the applicator and insert as far into the vagina as is comfortable (without forcing), or until half of the applicator is inside; discard the applicator after use; not use tampons or other vaginal products while using this product.

[figure not shown]
Figure 2 Gedeo Pessary and Applicator

Figure 3 Vaginal Tablet Applicator Label

Figure 4 Investigational Product Label

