5.3 Selection of Investigational Device and Doses

Refer to [Section 3.2](#)

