8.7	Proportion of patients having a reduction in the sum of the 3 BV symptoms scores	22
8.8	Recurrence rate	22
8.9	Proportion of patients receiving prolonged treatment.....	22
8.10	Proportion of patients receiving rescue treatment on Day 14	22
8.11	Compliance/Exposure.....	23
9	References	23
10	Signoff	24

1 Abbreviations

Abbreviation	Explanation
ADE	Adverse device effect
AE	Adverse event
ASADE	Anticipated serious adverse device effect
ATC	Anatomical Therapeutic Chemical [classification system]
BV	Bacterial vaginosis
CI	Confidence interval
CIP	Clinical Investigation Plan QRS-CL2-003, Version 2.0
CRF	Case report form
DDP	Data display plan
FAS	Full analysis set
GDL	Glucono-delta-lactone
ICH	International Council for Harmonisation of Technical Requirements for Pharmaceuticals for Human Use
ISO	International Organization for Standardization
MedDRA	Medical Dictionary for Regulatory Activities
NaG	Sodium gluconate
PP	Per-protocol analysis set
SADE	Serious adverse device effect
SAE	Serious adverse event
SAP	Statistical analysis plan
USADE	Unanticipated serious adverse device effect
WHO	World Health Organisation

2 Introduction

The Statistical Analysis Plan (SAP) is a complementary document to the Clinical Investigation Plan and includes a more technical and detailed elaboration of the principal features of the proposed statistical analysis and presentations, and the way in which anticipated analysis problems will be handled.

The Investigational product, Gedeo Pessary (commercial name *pHyph*), a slow-release formulation administering 300 mg GDL and 367.5 mg NaG over 45 hours, is generally denoted “treatment” in the SAP.

3 Study objectives

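### Second-course doses are fixed on Days 7, 9, 11 and 13, but the visit that starts the course may fall on Day 8 or 9 and no rule covers a late visit

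*Protocol*

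**What the plan says.** **Second course.** Women not cured at the visit described in Protocol Section 3.5.5 "receive additional doses of investigational product to be administered at home on Day(s) 7, 9, 11, and 13". Section 3.1, Table 3 and the footnote to Section 3.2 ("And on Day(s) 7, 9, 11, and 13 if receiving prolonged treatment") list the same days. Under Section 3.5.1 the Day 0 supply covers the first course only, so the second-course supply is available only from the Section 3.5.5 visit.

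**Windows.** Table 3 and Section 3.5.5 give that visit a window of +2 days, so Day 7, 8 or 9. For women on the second course, the next examination (Section 3.5.10) is also +2 days, so Day 14, 15 or 16. Sections 3.5.3 and 3.5.7 say what happens when the Day 4 or Day 11 telephone contact is late: the dose stays on its nominal day. Section 3.5.5 has no such statement.

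**Definitions that depend on the schedule.** Protocol Section 5.1 plans 4 pessaries per woman, or 8 with prolonged treatment, and SAP Section 7.8 uses 4 and 8 as the expected doses for compliance. SAP Section 8.9 counts a woman as having received prolonged treatment if she took a dose on Day 7, 9, 11 or 13.

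**Rationale and content.** Section 3.2 supports the spacing by an in vitro dissolution test that "showed a pH-decrease duration of approximately 45 hours". Section 5.3 gives no dose rationale of its own and points back to Section 3.2. The NaG content in Section 3.2 is 376.5 mg ("The dose of 300 mg GDL and 376.5 mg NaG administered 2 days apart on Day(s) 0, 2, 4, and 6"). The synopsis ("Gedea Pessary, containing 300 mg GDL and 367.5 mg NaG, administered vaginally"), Protocol Section 5.1 ("administering 300 mg GDL and 367.5 mg NaG over 45 hours") and the SAP introduction ("a slow-release formulation administering 300 mg GDL and 367.5 mg NaG over 45 hours") give 367.5 mg.

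**The concern.** A woman seen on Day 8 or 9 cannot take a pessary on Day 7 from a supply she does not yet have. The visit window and the fixed dosing days are both stated rules, and for such a woman they cannot both be followed. Each site would have to choose: keep the remaining listed days and lose a dose, or move the whole course.

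The choice affects what is reported for the second course. Day 14 cure would mix women examined after 3 second-course doses with women examined after 4, and nothing planned links the cure result to the doses taken before the examination. Under the SAP's calendar-day definition, a woman treated throughout could be counted as not prolonged. SAP Section 7.2.1 forms separate sub-populations by prolonged treatment. If Section 8.9 decides membership, which the SAP does not say, she would also drop out of the Day 14 analyses.

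Two smaller points sit in the same dose-selection text. The rationale does not address the 1-day step from Day 6 to Day 7, and its NaG figure differs from the other three places.

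**Working it through.** **Inputs.** First-course days 0, 2, 4, 6 and second-course days 7, 9, 11, 13 (Protocol 3.1, 3.2 with footnote, 3.5.5). Day 7 visit +2 days and Day 14 examination +2 days (Table 3, 3.5.5, 3.5.10). Expected doses 4 or 8 (SAP 7.8). Follow-up of 29 days after last treatment (Protocol 3.1). Cure rate 70% and 24 patients (Protocol 9.3). In vitro duration about 45 hours (Protocol 3.2).

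**Step 1: the plan's own figure.** Last contact minus last dose is 35 − 6 = 29 days without and 42 − 13 = 29 days with prolonged treatment. The 29 days reproduce, so the figure assumes last doses exactly on Day 6 and Day 13.

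**Step 2: each permitted visit day.** With the listed days kept, doses taken are the 4 first-course doses plus the listed days not yet past. With a shifted course at 2-day spacing (an assumption, since the documents give no rule), doses fall on v, v + 2, v + 4 and v + 6 for a visit on Day v. An examination on the same day as the last dose is not counted as following it.

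| Visit day | Listed days still possible | Doses of 8 expected, listed days kept | Shifted course | Shifted doses on a listed day | Examination days after last shifted dose | Last shifted dose to Day 42 |
|---|---|---|---|---|---|---|
| 7 | 7, 9, 11, 13 | (4 + 4)/8 = 100% | 7, 9, 11, 13 | 4 | 14, 15, 16 | 42 − 13 = 29 days |
| 8 | 9, 11, 13 | (4 + 3)/8 = 87.5% | 8, 10, 12, 14 | 0 | 15, 16 | 42 − 14 = 28 days |
| 9 | 9, 11, 13 | (4 + 3)/8 = 87.5% | 9, 11, 13, 15 | 3 | 16 only | 42 − 15 = 27 days |

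For a Day 8 start the shifted course meets none of the days in SAP 8.9, so the literal classification is not prolonged. It also conflicts with Protocol 3.5.7, which keeps a dose on Day 11. For a Day 9 start the classification is right, but an examination on Day 14 would follow only the doses of Days 9, 11 and 13.

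**Step 3: how many women.** Expected to enter the second course: 24 × (1 − 0.70) = 7.2, about 7. With 7 women, one changed classification or outcome moves a proportion by 1/7, about 14 percentage points. The share seen on Day 8 or 9 is not given and cannot be derived.

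**Step 4: the interval in the rationale.** Gaps between listed dose days are 2, 2, 2, 1, 2, 2, 2 days. At equal clock times (an assumption), Day 6 to Day 7 is 24 hours against about 45, so the two periods overlap by 45 − 24 = 21 hours. A start on Day 8 or 9 leaves 48 or 72 hours and no overlap. The 1-day step and the late-visit conflict therefore never occur in the same woman.

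**Step 5: NaG.** 376.5 − 367.5 = 9 mg, and 9/367.5 = 2.4%.

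**The case against.** The strongest reply is that this is one missing sentence about late visits, plus a digit slip. Much of it stands.

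- A reader might infer that a late visit forces the examination before the last dose. It does not. The Day 14 examination has its own +2 days, so a Day 8 start fits an examination on Day 15 and a Day 9 start fits one on Day 16, each keeping the planned one-day gap. But the documents do not tie the second window to the first, so the order is left to chance.
- A reader might infer that Section 3.2 contradicts the other sections on the dosing interval. It does not. Its first-course spacing agrees with the synopsis, and the second-course days are the same throughout. The rationale is silent on one step, which is a gap and not a contradiction.
- A reader might take the 21-hour overlap as a safety finding. The 45 hours in Section 3.2 is an in vitro result, no passage makes non-overlap a condition of tolerability, and the Investigator's brochure cited there is not available here.
- The NaG mismatch is close to clerical. The pessary is supplied ready-made in blisters, so no site measures NaG. The documents alone still do not settle which figure is right.
- Day 14 cure is a secondary estimate without a hypothesis test (SAP 7.9.2), and SAP 7.8 would show a missed dose in the compliance rate. It would not show when doses were taken relative to the examination.

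What the reply does not remove is that two stated rules cannot both be followed after a Day 8 or 9 visit, and that the SAP definition fails under one natural way of resolving them.

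**Conclusion.** The point holds for the second course. After a Day 8 or 9 visit, four second-course doses cannot be taken on the listed days. Keeping those days gives at most 3 of 4 (7 of 8 overall). Shifting the course at 2-day spacing, which is an assumption, either puts the woman outside SAP 8.9 (Day 8 start) or puts her last dose on Day 15, before the examination only if that is held on Day 16 (Day 9 start). Day 14 cure may therefore be read after 3 or 4 second-course doses.

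The reach is limited. Day 7 cure is assessed before any second-course dose, so the primary endpoint and the sample size are unaffected. A reader might take the 7 women expected to enter the second course as the number affected, but that is everyone expected not to be cured at the assumed 70% rate. Only those seen late meet the window conflict, and their number is not known. The unaddressed Day 6 to Day 7 step and the 9 mg NaG difference are secondary matters of reconciliation. The correction should be made, because it is cheap and settles how the second course is run, classified and reported.

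**What to change.** **Protocol.** The sponsor must reconcile three things: the Day 7 and Day 14 windows with the second-course dosing days; the rationale in Section 3.2 with the schedule used, including the step from Day 6 to Day 7; and the NaG figures in Section 3.2, Section 5.1, the synopsis and the SAP. No dose or schedule is proposed here.

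**SAP.** In Section 8.9, define receipt of prolonged treatment as having taken at least one dose of the second-course supply, instead of by listed calendar days. State that the sub-populations in Section 7.2.1 use this definition. Report Day 14 cure together with the number of second-course doses taken before the examination.

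**Data.** Record the date of each second-course dose. Protocol Section 5.8 says that women are asked about administration but does not say that dates are collected, so this may need a small eCRF addition.

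**Cost.** Wording changes, at most one set of date fields, and one descriptive breakdown in about 7 women. No extra patients or visits are needed.

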3.2.1 Risks and Benefits

The investigational device, Gedea Pessary has been evaluated in accordance with ISO 10993 (Biological Evaluation of Medical Devices). The evaluation included: cytotoxicity testing (Direct cell contact test, ISO 10993-5); *in vivo* irritation (Vaginal acute irritation; ISO 10993-10); and sensitization (local lymph node assay, ISO 10993-10). The *in vitro* cytotoxicity test, classified the test item as slight to moderate cytotoxic (scale 1–2 on a 3-grade scale); the *in vivo* irritation test as well as the *in vivo* sensitization test showed no signs of irritation, necrosis, or sensitization after treatment with Gedea Pessary.

The vaginal pessary may, in similarity with other vaginally administered products, cause temporary minor discomfort at insertion. The vaginal sampling procedures are similar to sampling procedures used in clinical practice and are unlikely to cause any major inconvenience to patients. In the Laccure pessary study,³⁸ there were no SAEs and vaginal itching was the most common AE.

There is a risk that patients will have no clinical benefit from the investigational device. This may cause patients to experience symptoms of BV including vaginal fishy smell, burning or irritation, pain during sexual intercourse, pain or discomfort when urinating, or abnormal vaginal discharge longer than necessary. However, an antibiotic will be offered on Day 14 if any symptoms should still be present, thus avoiding any risk associated with long-term untreated BV.

Subjects included in the study must refrain from using other intravaginal products to mitigate any risk of interactions with concomitant vaginally-administered products. The investigational

^a And on Day(s) 7, 9, 11, and 13 if receiving prolonged treatment

Protocol Version 2.1, 27 Jun 2019

LINK Medical Research | Protocol template

Version 2.0 | Effective date 17Apr2018

device acts locally on the vaginal mucosa and most likely will most likely not affect any concomitant systemic treatment.

Taken together, as the anticipated levels of discomfort are transient and mild, and that risks associated with long-term untreated BV are avoidable, the use of the investigational product appears to offer clinical benefits at a reasonable risk level.

3.3 Recruitment

Patients will be recruited at study sites' gynecological clinics. Post-menarchal, pre-menopausal females 18 years or older seeking for BV symptoms (fishy smell, irritation, and burning) may be informed verbally and in writing about the study and screened following signed informed consent. Patients may also be pre-informed about the study by the use of advertisement through social media; these patients will directly book appointments with the clinic. The recruitment of patients will start only after the approval of the clinical investigation plan (CIP) by the regulatory authorities (RA) and the independent ethics committee (IEC). No study procedures will be performed unless the patient has provided written informed consent to study participation. See also [Section 4.1](#).

